8.4 Secondary Efficacy Analyses

8.4.1 Key Secondary Efficacy Analyses

8.4.1.1 Change from Baseline in DYS, NMPP, Dyspareunia, and Overall Endometriosis-Associated Pain

The change from baseline in DYS, NMPP, dyspareunia, and Overall endometriosis-associated pain at Months 3, 6, and 12 will be evaluated with mixed-effects model repeated measures (MMRM) analysis. The MMRM analysis will include the fixed categorical effects of treatment, visit, and treatment-by-visit interaction, and continuous fixed covariate of baseline score. A random subject effect term is included to account for the correlation among the repeated measurements in the changes from baseline. The

following covariance structures will be used to estimate the within subject errors in preliminary analyses for the changes from baseline to each scheduled visit: Spatial Power, Compound Symmetry, and Unstructured. For each efficacy parameter, the covariance structure converging to the best fit, as determined by the smallest value for the Akaike Information Criterion (AIC), will be used as the covariance structure in the MMRM analysis for that efficacy parameter. The LS mean and standard error will be reported for each treatment group; the LS mean of treatment difference and associated 95% CI and P value will be reported comparing elagolix plus E2/NETA group against placebo group.

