2.4 Sample Size Determination

This study plans to enroll approximately 700 subjects, with 400 subjects in the elagolix 200 mg BID plus E2/NETA (1 mg/0.5 mg) QD, 100 subjects in the elagolix 200 mg BID, and 200 subjects in placebo, representing a randomization ratio of 4:1:2. These sample sizes were chosen to ensure a sufficient number of subjects completing 12 months of total treatment with elagolix during the placebo-controlled treatment period for the evaluation of safety assessment. Assuming Non-Menstrual Pelvic Pain (NMPP) responder rates of 54% for the elagolix with E2/NETA therapy dose group and 35% for placebo, and

Dysmenorrhea (DYS) responder rates of 59% for the elagolix with E2/NETA therapy dose group and 23% for placebo, these sample sizes provide greater than 90% power to detect a difference in response rate between elagolix with E2/NETA and placebo for both DYS and NMPP, based on a 2-sided test at the significance level of $\alpha = 0.05$.

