8.2 Handling of Missing Data

Missing data will be imputed using the following methods for the efficacy analyses:

- Last Observation Carried Forward (LOCF): The LOCF analyses will use the completed evaluation from the previous post-baseline evaluation to impute missing data at the current evaluations. Values will only be carried forward if a subject prematurely discontinues and if the analysis month is equal to or after the month in which the subject prematurely discontinued. For Month 1 analysis, only observed cases will be used.
- Mixed-Effect Model Repeat Measurement (MMRM): The repeated measures analysis will be conducted using a mixed model including observed measurements at all visits. The mixed model includes the categorical fixed effects of treatment, visit and treatment-by-visit interaction, and the continuous fixed covariate of baseline measurement. An unstructured variance covariance matrix will be used. Parameter estimation is based on the assumption of data being missing at random and using the method of restrictive maximum likelihood (REML).
- Observed Cases (OC): The OC analysis will not impute values for missing evaluations, and thus a subject who does not have an evaluation on a scheduled visit will be excluded from the OC analysis for that visit. OC will exclude values after a subject prematurely discontinues from study drug.

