8.5 Additional Efficacy Analyses

8.5.1 Endpoints related to DYS, NMPP, Dyspareunia and Overall endometriosis-associated pain

The proportion of responders at Months 1 – 12 based on change from baseline in average pain scores (DYS, NMPP, or dyspareunia) and analgesic use criteria (as defined in [Table 1](#)) will be analyzed using a logistic regression model with the responder/non-responder categorization as the dependent variable, treatment as the main effect, and baseline pain score (DYS, NMPP or dyspareunia) as a covariate. The proportion of responders, difference in proportions between elagolix plus E2/NETA group and placebo group, and odds ratio with corresponding 95% CI and P values will be presented. The pain threshold for defining responders will be determined using the same ROC analysis

described for the co-primary endpoints. Details of the ROC analysis are presented in [Appendix A](#) and the pain threshold values (X) are presented in [Appendix C](#). The same analyses will be repeated for the proportion of responders at Months 1 – 12 based only on change from baseline in average pain scores (DYS, NMPP, or dyspareunia). The responder analysis will be using the LOCF approach.

In addition, the proportion of responders at Months 1 – 12 based on change from baseline in average pain scores (DYS, NMPP, or dyspareunia) and analgesic use criteria and proportion of responders based on change from baseline in average pain scores (DYS, NMPP, or dyspareunia) only will also be summarized by treatment group using observed cases.

The change from baseline to each month in *DYS*, *NMPP*, *Dyspareunia*, and overall endometriosis-associated pain during the 12-month placebo-controlled Treatment Period will be evaluated using MMRM analysis. The MMRM analysis will include the fixed categorical effects of treatment, visit, and treatment-by-visit interaction, and the continuous fixed covariate of baseline pain score. A random subject effect term is included to account for the correlation among the repeated measurements in the changes from baseline. The selection and use of the covariance structure used in this analysis will follow the same process as described previously for the ranked secondary endpoints in [Section 8.4.1.1](#). The LS mean and standard error will be reported for each treatment group; the LS mean of treatment difference and associated 95% CI and P value will be reported comparing elagolix plus E2/NETA group against placebo group.

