8.5.2 Rescue Analgesic Use for Endometriosis-Associated Pain

The monthly average rescue medication pill counts as collected in the e-diary will be summarized using observed cases only with descriptive statistics by treatment group for the categories of analgesic use – NSAIDs, opioids, any class of analgesic medications (NSAIDs or opioids), and both classes of analgesic medications (NSAIDs and opioids) during the 12-month placebo-controlled Treatment Period.

For the following categories of analgesic use – NSAIDs, opioids, any class of analgesic medications (NSAIDs or opioids), and both classes of analgesic medications (NSAIDs and opioids), the change from baseline to each month during the 12-month placebo-controlled Treatment Period will be evaluated using an MMRM analysis. The MMRM analysis will include the fixed categorical effects of treatment, visit, and treatment-by-visit interaction, and the continuous fixed covariate of baseline analgesic use. A random subject effect term is included to account for the correlation among the repeated measurements in the dependent variable. The selection and use of the covariance structure used in this analysis will follow the same process as described previously for the ranked secondary endpoints in Section 8.4.1.1. The LS mean and standard error will be reported for each treatment group; the LS mean of treatment difference and associated 95% CI and P value will be reported comparing elagolix plus E2/NETA group against placebo group. In addition, the change from baseline to each monthly visit during the 12-month placebo-controlled Treatment Period will be summarized by treatment group using observed cases.

Proportion of responders based solely on the change from baseline in analgesic use will be summarized by treatment group at each visit during the 12-month placebo-controlled Treatment Period using the observed cases. Definition of analgesic use responder will be based on Table 1. In addition, the proportion of responders will be analyzed using a chi-square test based on LOCF approach. The difference in proportions between elagolix plus

E2/NETA group and placebo group, and odds ratio with corresponding 95% CI and P values will be presented.

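### SAP 8.2 fixes an unstructured MMRM, but SAP 8.4.1.1 lets AIC choose the covariance for 12 of the 14 ranked tests and adds a random subject effect that two of its three candidates cannot identify

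*SAP*

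**What the plan says.** SAP 8.2 (Handling of Missing Data) describes the MMRM for the efficacy analyses: "The repeated measures analysis will be conducted using a mixed model including observed measurements at all visits". Its terms are treatment, visit, treatment-by-visit and baseline, fitted by REML. On covariance it says "An unstructured variance covariance matrix will be used". It lists no random subject effect and makes no exception for particular endpoints.

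SAP 8.4.1.1 covers change from baseline in DYS, NMPP, dyspareunia and overall endometriosis-associated pain at Months 3, 6 and 12. It has the same fixed effects but adds: "A random subject effect term is included to account for the correlation among the repeated measurements in the changes from baseline". Three structures are then tried in preliminary fits (Spatial Power, Compound Symmetry, Unstructured), and the choice is made separately per pain measure by this rule: "the covariance structure converging to the best fit, as determined by the smallest value for the Akaike Information Criterion (AIC), will be used".

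SAP 8.5.1 repeats the random effect and refers back to 8.4.1.1. SAP 8.5.2 (rescue analgesic use) says "A random subject effect term is included to account for the correlation among the repeated measurements in the dependent variable" and that its covariance choice "will follow the same process as described previously for the ranked secondary endpoints in Section 8.4.1.1". So every MMRM that the SAP specifies in detail follows 8.4.1.1. The protocol (Synopsis and 8.1.6.3) names the MMRM but no covariance structure.

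**The concern.** Two programmers could each follow the SAP and report different p-values for the same ranked test. SAP 3.2 ranks 14 secondary endpoints, and 12 of them (ranks 1-6, 8-10 and 12-14) use this model. The two PROMIS tests (ranks 7 and 11) use ANCOVA and fall outside the point, as do the logistic co-primaries.

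The 8.4.1.1 rule has two faults of its own:

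- The random subject effect duplicates what Compound Symmetry and Unstructured already contain.
- Unstructured is the only candidate that lets variance differ between months. When AIC rejects it on parameter count, the standard errors at Months 3 and 12 both rest on a variance averaged over the year. If variance changes over the year, they are wrong in opposite directions.

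SAP 10.0 tests in fixed sequence, so a changed verdict at rank 8 (dyspareunia, Month 12) would open or close ranks 9-14.

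**Working it through.** **The plan's own power figure.** SAP 2.4 assumes DYS "responder rates of 59% for the elagolix with E2/NETA therapy dose group and 23% for placebo", and NMPP rates of 54% and 35%, with 400 and 200 subjects and two-sided 0.05. For NMPP the pooled rate is (400×0.54 + 200×0.35)/600 = 0.4767. The null SE is √(0.4767×0.5233×(1/400+1/200)) = 0.0433. The alternative SE is √(0.54×0.46/400 + 0.35×0.65/200) = 0.0419. Power = Φ((0.19 − 1.96×0.0433)/0.0419) = Φ(2.51) = 99.4%. The same steps for DYS give more than 99.99%. The stated figure of greater than 90% reproduces. No power is stated for the MMRM endpoints.

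**Identifiability.** With 12 monthly visits the total covariance is V = σ_b²J + R(θ), where J is the all-ones matrix. The rank of ∂V/∂(σ_b², θ) is:

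- Unstructured: R has 12×13/2 = 78 free entries, and adding σ_b² gives 79 parameters with rank 78.
- Compound Symmetry: R already contains a multiple of J, so 3 parameters have rank 2.
- Spatial Power: 3 parameters with rank 3, so identifiable.

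**AIC penalty.** Unstructured is charged 2×78 = 156, against 2×2 = 4 for Compound Symmetry (random effect absorbed) or 2×3 = 6 for Spatial Power with the random effect. It must improve −2 log-likelihood by more than 152 or 150 to be chosen.

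**Level if a constant-variance structure is kept.** Assume variance moves linearly from 1 at Month 1 to q at Month 12. The fitted variance is about (1+q)/2, and the level at month m is about 2[1 − Φ(1.96√(((1+q)/2)/v_m))]. For q = 1.3 the fitted variance is 1.15:

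- Month 12: v = 1.30, 1.96×√(1.15/1.30) = 1.84, level 6.5%.
- Month 6: v = 1 + 0.3×5/11 = 1.136, 1.96×√(1.15/1.136) = 1.97, level 4.9%.
- Month 3: v = 1 + 0.3×2/11 = 1.055, 1.96×√(1.15/1.055) = 2.05, level 4.1%.

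**How often AIC keeps constant variance.** Simulated with 400 vs 200, complete data, 200 data sets per scenario, REML AIC and three assumed correlations: 0.6 throughout; 0.4 + 0.6×0.7^lag; 0.9^lag. Ranges are across the correlations.

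| Variance, Month 1 to 12 | Constant variance kept | Month 3 level | Month 6 level | Month 12 level |
|---|---|---|---|---|
| Constant | 100% | 4.9-5.0% | 4.9-5.0% | 4.9-5.0% |
| Rises 1.1 times | 100% | 4.64-4.69% | 4.94-4.99% | 5.53-5.59% |
| Rises 1.2 times | 100% | 4.28-4.34% | 4.83-4.90% | 5.97-6.05% |
| Rises 1.3 times | 97-100% | 4.04-4.09% | 4.83-4.88% | 6.45-6.53% |
| Rises 1.5 times | 16.5-69.5% | 4.07-4.79% | 4.89-5.07% | 5.38-6.58% |
| Rises 2 times | 0% | as Unstructured | as Unstructured | as Unstructured |
| Falls 1.3 to 1 | 96.5-100% | 5.90-5.91% | 5.08-5.10% | 3.51-3.60% |

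Fixed Unstructured gives 4.88-5.10% throughout. A separate simulation (1,500 runs per scenario, two correlation shapes) agrees on the selection pattern, with large-sample Month 12 levels of 5.55%, 6.06% and 6.53% at 1.1, 1.2 and 1.3 times. With 30% completely random dropout by Month 12 (40 data sets per scenario), the Month 12 levels at 1.1, 1.2 and 1.3 times are 5.67-5.80%, 6.18-6.30% and 6.83-6.88%, against 4.99-5.34% for Unstructured.

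**Opposite verdicts at Month 12** (AIC-selected model and fixed Unstructured on different sides of 0.05):

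| Variance | 50% power | 90% power | 99% power |
|---|---|---|---|
| Constant | 1.31-1.38% | 0.58-0.61% | 0.09% |
| Rises 1.3 times | 4.36-4.67% | 1.80-1.95% | 0.26-0.29% |
| Falls 1.3 to 1 | 5.68-5.79% | 2.73-2.79% | 0.45-0.46% |

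**At the planned effects**, converting responder rates by probit and assuming they hold at Month 12: DYS 0.966 SD and NMPP 0.486 SD. With √(1/400+1/200) = 0.0866, z = 11.16 and 5.61. Opposite verdicts are effectively nil for DYS and 0.002-0.010% for NMPP.

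**The case against.** The best defence is that 8.2 is a generic description under a missing-data heading. On the usual reading that the specific section overrides the general one, 8.4.1.1 governs and no test lacks a rule. That is probably how the SAP was meant, but it never says so, and 8.2 carries no exception clause.

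The AIC rule is prespecified and mechanical, with named candidates and one criterion. That stands: this is not an unplanned choice. The rule also corrects itself for large variance changes, since Unstructured is always chosen at a twofold rise.

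The redundant random effect leaves the total covariance identified, so treatment estimates survive if the software sets that variance to zero. Also true. What remains is a possible convergence failure under a rule that requires convergence, and a 2-point AIC ambiguity depending on whether the redundant parameter is counted. Neither effect was measured here.

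Finally, the variances, correlations and dropout are assumed, and even the direction of the variance change is unknown; a fall makes Month 12 conservative. The levels above show what the rule permits. They do not demonstrate inflation in this trial.

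**Conclusion.** The concern holds and is minor. The contradiction between 8.2 and 8.4.1.1 and the non-identifiability under two of three candidates follow from the text and algebra and need no assumption. The size of the AIC effect does rest on assumptions: linear variance change, three correlation shapes, 12 visits and 400 vs 200. Within them, a rise of 1.1 to 1.3 times puts the Month 12 level at about 5.5-6.5% with complete data and up to 6.9% with 30% dropout. Month 6 is hardly affected.

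DYS (ranks 1-3) and NMPP (ranks 4-6) verdicts cannot plausibly change at the planned effects. The exposure is a marginal result in dyspareunia (ranks 8-10) or overall pain (ranks 12-14), for which the documents state no planning effect. Nothing in them shows that either is marginal.

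**What to change.** **If the Month 12 analysis has not been run:** state one model in SAP 8.2 and 8.4.1.1, namely MMRM with unstructured covariance, no random subject effect, REML and Kenward-Roger degrees of freedom (neither section names a degrees-of-freedom method). Add a fallback used only on non-convergence: the first that converges of heterogeneous Toeplitz, heterogeneous first-order autoregressive, compound symmetry. Delete the AIC selection, and the random-effect sentences in 8.5.1 and 8.5.2.

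**If it has been run:** Protocol 5.3.1.1 (Endometrial Biopsy) says all subjects are past Month 36 at Amendment 7, so this is likely. Do not change the model. Keep the prespecified 8.4.1.1 result, correct 8.2 by a cross-reference to it, report the structure selected for each of the four pain measures, and show the fixed-unstructured result beside it as a sensitivity analysis.

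The cost is wording in four SAP sections or, in the second case, one cross-reference and four extra model runs. No new data are needed. The drawback of Unstructured is its 78 covariance parameters, which is why the fallback is there.

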8.4.1.2 Change from Baseline in PROMIS Fatigue Short Form 6a T-Score

The PROMIS Fatigue Short Form 6a will be summarized as observed. Missing data will not be imputed. The change from baseline in PROMIS Fatigue Short Form 6a T-score at Month 6 and 12 will be evaluated using ANCOVA with treatment as the main effect and baseline score as a covariate. The LS mean and standard error will be reported for each treatment group; the LS mean of treatment difference and associated 95% CI and P value will be reported comparing elagolix plus E2/NTEA group against placebo group.

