Analysis details for Months 1-12 and Months 13-48 of the treatment period will be specified in the statistical analysis plan (SAP). No statistical tests will be performed following the 12-month placebo-controlled portion of the 48-month Treatment Period. Data from subjects randomized to the elagolix 200 mg BID alone will be summarized separately from subjects randomized to the elagolix 200 mg BID plus E2/NETA (1 mg/0.5 mg) QD arm. Unless otherwise specified, no statistical tests will be performed to evaluate potential differences between the two elagolix dose groups.

The mean change from baseline in key secondary endpoints will be analyzed using a mixed-effects model with repeated measures. Key secondary endpoints will be assessed at Month 3, Month 6 or Month 12. Other efficacy endpoints and analyses will be defined in the SAP.

For subjects randomized to placebo in the first 12 months of the treatment period, baseline will be re-set to the data collected the month prior to the first dose of elagolix in Months 13 - 48 of the treatment period. For subjects randomized to either one of the elagolix treatment groups, baseline for these subjects will refer to the baseline prior to the first dose of elagolix at the time of randomization.

Statistical Methods (Continued):

BMD Assessments:

The key BMD comparisons are in lumbar spine at Month 6 and Month 12. Secondary BMD endpoints include total hip and femoral neck. The elagolix 200 mg BID plus E2/NETA (1 mg/0.5 mg) QD dose will be compared to placebo at Months 6 and 12 and will be compared to elagolix 200 mg BID alone at Month 6 based on percent change from baseline. Percent change in BMD from baseline values, as well as Z-scores and T-scores at all time points will also be summarized. Analysis details will be provided in the SAP.

Safety Assessments:

All subjects who receive at least 1 dose of study medication will be included in the safety analyses. Hematology, chemistry (including lipid panel), urinalysis, vital signs, endometrial assessments and uterine bleeding variables will be summarized. Changes from Baseline to each Treatment Period visit during the first 12 months of treatment will be analyzed using an ANOVA or ANCOVA model as appropriate as specified in the SAP.

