8.1.6.3 Other Efficacy Variables

Other efficacy endpoints during the treatment period will include the following (in no particular order).

- Proportion of responders as assessed by change from Baseline in average pain score and analgesic use monthly for DYS, NMPP and dyspareunia, respectively.
- Proportion of responders as assessed by change from Baseline in average pain score alone (i.e., not taking into consideration of analgesic use) monthly for DYS, NMPP and dyspareunia, respectively.
- Change from Baseline, in the monthly average pain score (DYS, NMPP, and dyspareunia), as assessed using information from the e-Diary.
- Change from Baseline in analgesic use (average pill counts) to treat endometriosis-related pain, as assessed using information from the e-Diary monthly.
- Proportion of analgesic use responders monthly (based only on reduction of rescue analgesics used).
- Monthly response in the PGIC and overall endometriosis-associated pain questionnaire.
- Change from baseline for each of six domains of EHP-30 questionnaire scores.
- Change from baseline for the EuroQoL-5D (EQ-5D-5L).
- Change from baseline for the WPAI:SHP.
- HCRU at each scheduled assessment.

• Change from baseline for the PROMIS Fatigue short Form 6A T-Score.

The analyses for those other efficacy endpoints will be conducted at an alpha level of 0.05 without multiplicity adjustment. 95% CIs will be constructed as needed. Analysis details will be specified in the SAP.

Statistical Analyses for Secondary and Other Efficacy Variables

Generally, for continuous variables, including change from baseline analyses, treatment group differences will be analyzed as appropriate using analysis of covariance (ANCOVA) models with treatment group as the main effect and baseline score as a covariate. The mixed model with repeated measures (MMRM) method for change from baseline to each post-baseline assessment during the placebo controlled Treatment Period will be conducted as appropriate.

Categorical data will be analyzed using CMH test, chi-square, Fisher's exact test or logistic regression as appropriate.

During Months 13 - 48, visit values and change from baseline to each visit will be summarized by each group described in Section 8.1.1. No statistical tests of data from Months 13 - 48 will be performed.

Analysis details will be specified in the SAP.

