3.2 Secondary Endpoint(s)

The ranked secondary efficacy endpoints (elagolix plus E2/NETA versus placebo) will be tested in the following order:

1. Change from Baseline to Month 12 in DYS
2. Change from Baseline to Month 6 in DYS
3. Change from Baseline to Month 3 in DYS
4. Change from Baseline to Month 12 in NMPP
5. Change from Baseline to Month 6 in NMPP
6. Change from Baseline to Month 3 in NMPP
7. Change from Baseline to Month 6 in PROMIS Fatigue Short Form 6a T-Score
8. Change from Baseline to Month 12 in dyspareunia
9. Change from Baseline to Month 6 in dyspareunia
10. Change from Baseline to Month 3 in dyspareunia
11. Change from Baseline to Month 12 in PROMIS Fatigue Short Form 6a T-Score
12. Change from Baseline to Month 12 in Overall Endometriosis-Associated Pain
13. Change from Baseline to Month 6 in Overall Endometriosis-Associated Pain

14. Change from Baseline to Month 3 in Overall Endometriosis-Associated Pain

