In addition, the change from baseline to each month in *DYS*, *NMPP*, *dyspareunia*, and overall endometriosis-associated pain during the 12-month placebo-controlled Treatment Period will be summarized by treatment group using observed cases. The change from baseline to each monthly visit in overall endometriosis-associated pain during the open-label Treatment Period will also be summarized by treatment group using observed cases.

In addition, the following plots will be provided using observed cases:

- Cumulative distribution function for reduction from baseline in DYS, NMPP, and dyspareunia to Months 1 – 12.

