8.5.7 PROMIS Fatigue Short Form 6a

The PROMIS Fatigue Short Form 6a will be summarized and analyzed using observed cases. Missing data will not be imputed.

During the 12-month placebo-controlled Treatment Period, the change from baseline to each scheduled assessment for PROMIS Fatigue Short Form 6a T-score will be analyzed using ANCOVA with treatment as the main effect and baseline as a covariate. The LS mean and standard error will be reported for each treatment group; the LS mean of treatment difference and associated 95% CI and P value will be reported comparing elagolix plus E2/NETA group with placebo.

In addition, the change from baseline to each scheduled assessment for PROMIS Fatigue Short Form 6a T-score will be summarized with descriptive statistics during the Treatment Period. No comparisons or statistical tests will be performed.

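### The ranked Month 12 PROMIS Fatigue test uses observed-case ANCOVA that ignores Month 6 scores, so it can be biased if dropout depends on fatigue and differs by arm; the protocol synopsis names a repeated-measures model

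*SAP*

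**What the plan says.** SAP 3.2 puts "Change from Baseline to Month 6 in PROMIS Fatigue Short Form 6a T-Score" at rank 7 and the Month 12 change at rank 11 of 14. SAP 10.0 tests the list as a fixed sequence, so rank 11 gates ranks 12 to 14 (overall endometriosis-associated pain at Months 12, 6 and 3).

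SAP 8.4.1.2 says the PROMIS change at each of the two visits "will be evaluated using ANCOVA with treatment as the main effect and baseline score as a covariate", and on missing data: "The PROMIS Fatigue Short Form 6a will be summarized as observed. Missing data will not be imputed". SAP 8.5.7 repeats the approach: "The PROMIS Fatigue Short Form 6a will be summarized and analyzed using observed cases". SAP 8.2 adds that "OC will exclude values after a subject prematurely discontinues from study drug".

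The other 12 ranked endpoints are analysed by MMRM (SAP 8.4.1.1).

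The protocol speaks twice. The synopsis says: "The mean change from baseline in key secondary endpoints will be analyzed using a mixed-effects model with repeated measures", with no exception for PROMIS. Section 8.1.6.3, which covers secondary and other variables, says that for continuous variables "treatment group differences will be analyzed as appropriate using analysis of covariance (ANCOVA) models with treatment group as the main effect". It adds MMRM where appropriate and leaves details to the SAP.

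**The concern.** Two ranked tests depart from the method the synopsis names and from the method the SAP uses for the other 12. The SAP gives no reason and specifies no missing-data sensitivity analysis for PROMIS, whereas the co-primary endpoints have two (SAP 8.3.4, items 2 and 3).

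A woman who attends Month 6 and stops before Month 12 has a measured fatigue score that says something about where she was heading. A Month 12 ANCOVA restricted to women present at Month 12 makes no use of it. If tired women leave one arm more than the other, the remaining women no longer form a fair comparison. An error against the drug can stop the sequence before overall pain is tested. An error in its favour can let the sequence continue wrongly.

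**Working it through.** **1. The plan's own figure.** The only stated power, above 90%, is for the co-primary responder rates (protocol 8.2). It reproduces. For NMPP, 54% against 35% with 400 and 200 women:
- Pooled rate = (216 + 70)/600 = 0.477.
- Null SE = sqrt(0.477 × 0.523 × (1/400 + 1/200)) = 0.0433.
- Alternative SE = sqrt(0.54 × 0.46/400 + 0.35 × 0.65/200) = 0.0419.
- z = (0.19 - 1.96 × 0.0433)/0.0419 = 2.51, so power is 99.4%. DYS exceeds 99.9%.

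This does not bear on PROMIS. The documents give no SD, effect size, power or dropout rate for it.

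**2. Which data each method uses.** In the blinded period PROMIS is scheduled at Day 1, Month 6 and Month 12, plus the premature discontinuation visit (protocol Appendix C). Month 6 is the first scheduled post-baseline score, so a repeated-measures model has almost nothing extra to use there. At Month 12 it can use Month 6.

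**3. Where the bias comes from.** Write the Month 12 change as a linear function of treatment, baseline and Month 6 change, with coefficient d on the Month 6 change. If stopping depends on Month 6, the observed-case estimate equals the true effect plus d × (active minus placebo difference in how far staying shifts mean Month 6 change, given baseline). With equal SDs,

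d = (r612 - r0²)/(1 - r0²),

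where r612 is the Month 6 to Month 12 correlation and r0 the baseline to follow-up correlation. For 0.65 and 0.5, d = (0.65 - 0.25)/0.75 = 0.53. The bias is zero when the shift is the same in both arms, including when it is zero in both. A bias of 0.3 to 0.5 points needs a between-arm difference in shift of only 0.3/0.53 = 0.6 to 0.5/0.53 = 0.9 points.

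**4. Simulation, common slope in both arms.** From the documents: 400 against 200, two-sided 0.05. Assumed: SD 9, correlations 0.65 and 0.5, the same true effect at both visits, no loss before Month 6, and log-odds of stopping rising by 1 to 2 per SD of Month 6 worsening. The comparator is the likelihood estimate from both visits with treatment-by-visit and baseline-by-visit terms.

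| Dropout, active vs placebo | True effect | Observed-case ANCOVA | Two-visit model |
|---|---|---|---|
| 10% vs 21%, arm-specific intercepts | -2 | -1.5 to -1.7, power 54-62% | -2.0, power about 79% |
| 10% vs 29%, arm-specific intercepts | 0 | rejects 13-19% | rejects 5% |
| 18% vs 21%, one rule for both arms (slope 1) | -2 | -1.90 | -1.99 |
| Unrelated to Month 6 | -2 | -2.0 | -2.0 |

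**5. Simulation, selection confined to one arm.** Assumed: SD 10, correlations 0.7 and 0.5, 15% lost at random before Month 6, about 27-35% missing by Month 12, 3,000 trials per row. Positive bias is against the drug.

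| Selection on Month 6 | True effect | Bias, ANCOVA / two-visit | Rejection, ANCOVA / two-visit |
|---|---|---|---|
| None | 0 | 0.0 / 0.0 | 5.6% / 5.8% |
| Same in both arms | 0 | 0.0 / 0.0 | 5.4% / 5.4% |
| Placebo only | 0 | +0.9 / 0.0 | 17.0% / 5.5% |
| Active only | 0 | -0.9 / 0.0 | 18.8% / 5.1% |
| Same in both arms | -3 | +0.06 / -0.01 | 91% / 93% |
| Placebo only | -3 | +0.9 / 0.0 | 62% / 92% |
| Active only | -3 | -0.8 / 0.0 | 99% / 93% |

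Monte Carlo error on the rejection rates is about 0.4 percentage points near 5% and 0.7 near 18%.

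**The case against.** The best defence is that ANCOVA is permitted. Protocol 8.1.6.3 gives it as the general method and defers to the SAP, and the SAP is consistent within itself: monthly measures get MMRM, while sparsely scheduled questionnaires (EHP-30, EQ-5D-5L, WPAI:SHP, PROMIS) get observed-case ANCOVA. With two post-baseline visits, some of the preference for MMRM is taste. This stands to the extent that the conflict is with one sentence of the synopsis, not with the protocol as a whole. It does not explain why a gating test has no missing-data sensitivity analysis.

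Four stronger readings are tempting, and the documents do not support them:
- *The Month 12 test is biased.* Neither document gives a dropout rate or pattern, so the bias is only possible, and it can go either way.
- *ANCOVA is valid only if stopping is unrelated to Month 6 fatigue.* The rows with the same selection in both arms show otherwise: bias is 0.0 under no effect and 0.06 with a true effect of -3.
- *Both ranked PROMIS tests suffer.* Month 6 is the first scheduled post-baseline score, so rank 7 barely changes. The Month 6 scores are used in the rank 7 test; it is only the Month 12 test that ignores them.
- *The open-label pain ratings have the same fault.* Those data "open-label Treatment Period will also be summarized by treatment group using observed cases", which is descriptive, and no open-label tests are planned.

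It is also fair that the comparator above has a baseline-by-visit term, which the SAP's MMRM lacks. The simulations therefore support the model proposed below, not the SAP's MMRM wording as it stands.

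**Conclusion.** The point holds as a conditional weakness at rank 11, together with an inconsistency between the synopsis, protocol 8.1.6.3 and SAP 8.4.1.2. Two conditions must both be met for material bias: stopping between Months 6 and 12 depends on Month 6 fatigue, and either the dropout rate or that dependence differs by arm. Unequal dropout is plausible in a placebo-controlled trial that assumes responder rates of 54% against 35% and 59% against 23%, but it is not documented.

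Under the assumed inputs the error is about 0.3 to 0.9 T-score points in either direction, with type I error up to about 19% or power falling from about 79% to 54-62%. These sizes rest on assumed SDs, correlations, effects and dropout, and should be read as illustrative. If dropout is random or equally selective, the choice of model makes little difference.

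**What to change.** In SAP 8.4.1.2, make the ranked PROMIS analysis an MMRM of change at Months 6 and 12 with treatment, visit, treatment-by-visit, baseline and baseline-by-visit terms and an unstructured covariance. Read ranks 7 and 11 from its visit-specific contrasts. Keep the observed-case ANCOVA as a sensitivity analysis. Align SAP 8.5.7, the synopsis and protocol 8.1.6.3 so that all name the same method for this endpoint.

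The cost is SAP wording and one extra model on data already scheduled. When dropout is random almost nothing is lost (a power or error difference of a percentage point or two in the runs above). The limitation is that MMRM assumes data missing at random: it does not cover stopping that depends on fatigue not yet recorded, and the ANCOVA sensitivity analysis does not cover that either.

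Protocol 5.3.1.1 states that all subjects are past Month 36. If the 12-month analysis has already been unblinded, the MMRM should be reported as a labelled supportive analysis, with dropout between Months 6 and 12 shown by arm and by Month 6 change.
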